Non-interventional Study Protocol

Document Number:	c15931948-04
BI Study Number:	1160-0286
BI Investigational Product(s):	Dabigatran etexilate (Pradaxa®)
Title:	P atients' A sessment of S atisfaction for S troke Prevention in Atrial Fibrillation— I mpact of Conventional Oral Anticoagulant (Q AC) Compared with Novel Oral Anticoagulant (NO AC)
Brief lay title	PASSION
Protocol version identifier:	1.0
Date of last version of protocol:	15 March 2017
PASS:	No
EU PAS register number:	To be decided
Active substance:	B01AE07-Dabigatran etexilate
Medicinal product:	Dabigatran etexilate
Product reference:	EU/1/08/442 (EMA registration number)
Procedure number:	Not applicable
Marketing authorisation holder(s):	This study is initiated, managed, and financed by: Boehringer Ingelheim Division Medicine/Medical Affairs
Joint PASS:	No
Research question and objectives:	
Objective 1 To describe the treatment perception from patients with non-valvular atrial fibrillation (NVAF) receiving Pradaxa® or VKA for stroke prevention by using the self-estimation questionnaire of PACT-Q during a 6-month study period.
 
Objective 2 To investigate the patient's characteristics.

Proprietary confidential information © 2017 Boehringer Ingelheim International GmbH or one or more of its affiliated companies

Country(-ies) of study:	Taiwan
Author:	Title: of Medical Affairs Name: Tel: Direct Line: Fax:
Marketing authorisation holder(s):	Title: of Medical Affairs Name: Tel: Direct Line: Fax: Address:
MAH contact person in case of PASS:	Not applicable
EU-QPPV in case of PASS:	Not applicable
Signature of EU-QPPV in case of PASS:	Not applicable
Date:	15 March 2017
Page 2 of 49	
Proprietary confidential information © 2017 Boehringer Ingelheim International GmbH or one or more of its affiliated companies. All rights reserved. This document may not - in full or in part - be passed on, reproduced, published or otherwise used without prior written permission	

2. LIST OF ABBREVIATIONS

ADR	Adverse Drug Reaction
AE	Adverse Event
AESI	Adverse Event of Special Interest
AF	Atrial Fibrillation
ALT	Alanine Aminotransferase
AST	Aspartate Aminotransferase
AP	Alkaline Phosphatase
BI	Boehringer Ingelheim
CA	Competent Authority
CHA ₂ DS ₂ -VASc score	Congestive heart failure, Hypertension, Age (≥ 75), Diabetes mellitus, Stroke/TIA, Vascular disease, Age 65-74, Sex category
CI	Confidence Interval
CML	Clinical Monitor Local
CRA	Clinical Research Associate
CrCl	Creatinine Clearance
CRF	Case Report Form
DMP	Data Management Plan
EC	Ethics Committee
ENCePP	European Network of Centres for Pharmacoepidemiology and Pharmacovigilance
EU PAS Register	European Post- Authorization Study Register (current ENCePP electronic register of studies)
FDA	Food and Drug Administration
GCP	Good Clinical Practice
GEP	Good Epidemiological Practice
GPP	Good Pharmacoepidemiology Practice
HAS-BLED	Hypertension, Abnormal renal and liver function, Stroke (1 point), Bleeding history or predisposition, Labile INR, Elderly (> 65 years), Drugs and Alcohol
HRQoL	Health-Related Quality of Life
ICH	International Conference of Harmonisation
IEC	Independent Ethics Committee
INR	International Normalized Ratio
IRB	Institutional Review Board
ISF	Investigator Site File
MAH	Marketing Authorisation Holder
NHI	National Health Insurance
NIS	Non-Interventional Study
NSAID	Non-Steroidal Anti-Inflammatory Drug
NVAF	Non-Valvular Atrial Fibrillation
OAC	Oral Anticoagulation
PACT-Q [®]	Perception of Anticoagulant Treatment Questionnaire
PASS	Post-Authorization Safety Study
PT	Prothrombin Time
RWE	Real World Experience

SAE	Serious Adverse Event
SAP	Statistical Analysis Plan
SDV	Source Data Verification
SmPC	Summary of Product Characteristics
SOP	Standard Operating Procedure
SPAF	Stroke Prophylaxis (or Prevention) in Atrial Fibrillation
VKA	Vitamin K Antagonist

4. ABSTRACT

Name of company: Boehringer Ingelheim			
Name of finished medicinal product: Pradaxa® (Dabigatran etexilate) or Vitamin K Antagonist (VKA)			
Name of active ingredient: Dabigatran or VKA			
Protocol date: 15 March 2017	Study number: 1160-0286	Version/Revision: 1.0	Version/Revision date: 15 March 2017
Title of study:	Patients' Assessment of Satisfaction for Stroke Prevention in Atrial Fibrillation—Impact of Conventional Oral Anticoagulant (OAC) Compared with Novel Oral Anticoagulant (NOAC)		
Rationale and background:	Non-interventional studies (NIS) observing patients treated with Pradaxa® for stroke prevention in atrial fibrillation (SPAF) to assess treatment satisfaction have not been conducted in Taiwan. Due to the limited data on patients' perception of conventional Vitamin K antagonist (VKA) or Pradaxa® treatment in real world experience (RWE), it remains an interesting topic to address. Therefore, the observational study is proposed to describe the perception of anticoagulant treatment according to the questionnaire—PACT-Q in the cohorts of patients switching from VKAs to Pradaxa® or newly initiating Pradaxa®/VKAs.		
Research question and objectives:	Objective 1 To describe the treatment perception from patients with non-valvular atrial fibrillation (NVAF) receiving Pradaxa® or VKA for stroke prevention by using the self-estimation questionnaire of PACT-Q during a 6-month study period. Objective 2 To investigate the patient's characteristics.		
Study design:	This non-interventional study enrolling patients in Taiwan with a previous VKA therapy, followed by switching to Pradaxa® OR patients being newly diagnosed with NVAF and initiated on Pradaxa® or VKA. The study is primarily based on questionnaire—PACT-Q.		
Population:	Inclusion criteria: Cohort A (patients switched from VKA to Pradaxa®) 1.A. Written informed consent prior to participation. 2.A. Female or male patients ≥ 20 years of age with a diagnosis of non-valvular atrial fibrillation (NVAF). 3.A. At least 3 months of continuous VKA treatment for stroke		

	
prevention prior to baseline assessment.
 
4.A. Patients switched to Pradaxa® prior to baseline assessment according to the physician's discretion and the Summary of Product Characteristics (SmPCs)/reimbursement criteria.
 
OR
 
Cohort B (patients newly initiated Pradaxa® or VKA)
 
1.B. Written informed consent prior to participation.2.B. Female or male patients \geq 20 years of age, newly diagnosed with NVAF, and no previous treatment for stroke prevention (no use of any OAC within 1 year prior to enrolment).3.B. Patients initiated stroke prevention treatment with Pradaxa® or VKA according to the physician's discretion and the SmPCs/reimbursement criteria. 
Exclusion criteria:
 
1. Contraindication to the use of Pradaxa® or VKA as described in the SmPCs.2. Patients receiving Pradaxa® or VKA for any other condition than stroke prevention in NVAF.3. Current participation in any clinical trial of a drug or device.4. Current participation in an AF-related registry, e.g. the Gloria AF program. 
Withdrawal Criteria:
 
1. Patients withdraw informed consent.2. Patients lost to follow-up.3. Any pathological event, adverse event, or any change in the patient's status giving an indication to the physicians that further participation in the study may not be the best interest of the patient.
Variables:	
Primary outcome:
 
Cohort A (patients switched from VKA to Pradaxa®)
 
• Mean PACT-Q2 scores at the second (30-45 days) and the last assessment (150-210 days) compared to baseline assessment. 
Cohort B (patients newly initiated Pradaxa® or VKA)
 
• Mean PACT-Q2 scores at the second (30-45 days) and the last assessment (150-210 days) compared between 2 treatment groups. 
Secondary outcome:
 
Cohort A (patients switched from VKA to Pradaxa®)
 
• Mean PACT-Q2 score at the last assessment (150-210 days) compared to the second assessment (30-45 days). 
Cohort B (patients newly initiated Pradaxa® or VKA)
 
• Description of mean PACT-Q1 score at baseline.

	
Characterization of patients from both cohorts according to:
 
Demographics: Age, gender, race, education level, height, weight, and BMICo-morbiditiesConcomitant therapiesStroke- and/or bleeding related risk factors in the medical historyCHA₂DS₂-VASc scoreHAS-BLED scoreKidney function (creatinine clearance)Dosing of Pradaxa® and the reasons for dose changeDuration of previous VKA treatment (for Cohort A only)									
Data sources:	Source data are collected from medical charts and the questionnaires (PACT-Q) completed by the enrolled subjects at approximately 20 medical centers or regional hospitals. A case report form will be designed for data collection.									
Study size:	
It is planned that approximately total 1000 patients from around 20 medical centers or regional hospitals will be recruited in the study. An estimated sub-group allocation basing on real-world practice in Taiwan includes approximately 300 patients in Cohort A (patients switched from VKA to Pradaxa®) and around 700 patients in Cohort B (patients newly initiated Pradaxa® or VKA), with about 500 patients receiving Pradaxa® and 200 patients receiving VKA. Consecutive enrolment will be performed to minimize selection bias. The actual number of patients in each cohort will be according to the patient distribution in the real-world practice.
 

Total number	1000	

Estimated number in sub-grouping	Cohort A—VKA switches to Pradaxa®	300	

Cohort B—Newly initiator	Pradaxa® VKA	500 200	

	Total number		1000	Estimated number in sub-grouping	Cohort A —VKA switches to Pradaxa®	300	Cohort B —Newly initiator	Pradaxa® VKA	500 200
Total number		1000								
Estimated number in sub-grouping	Cohort A —VKA switches to Pradaxa®	300								
	Cohort B —Newly initiator	Pradaxa® VKA	500 200							

Data analysis:	
A Data Management Plan (DMP) and Statistical Analysis Plan (SAP) will be prepared to describe all processes, variables, and specifications for data collection, cleaning, validation, and analyses.

	
The study is essentially descriptive. All patients who have signed the informed consent and fulfilled study criteria will be included in the main analysis.

	
Baseline demographic and clinical characteristics Descriptive summary will be presented for all patients enrolled in Cohort A, Cohort B Pradaxa® initiators, and Cohort B VKA initiators, respectively. For continuous variables, number of patients, mean, standard deviation, median, lower quartile, upper quartile, minimum, and maximum will be presented. For categorical variables, frequency and percentage will be presented for each category.

Primary outcomes	
For Cohort A, the PACT-Q2 score at Visit 2 and Visit 3 will be compared with the PACT-Q2 score at baseline visit, respectively, using paired t-test or Wilcoxon signed-rank test.

	
For Cohort B, the patients newly initiated Pradaxa® or VKA will be matched with a ratio of 1:1 based on the propensity score. The covariates will be included in the propensity score model if available. Descriptive summary of the baseline characteristics will be compared between the matched patients to check the balance of baseline characteristics between the two sub-groups of Cohort B after propensity score matching (PSM). Standardized difference will be calculated as a measure of the balance of baseline characteristics after PSM. Analyses of PACT-Q2 score will be performed on propensity score matched Pradaxa® initiators and VKA initiators. PACT-Q2 score will be compared between matched Pradaxa® initiators and VKA initiators using paired t-test or Wilcoxon signed-rank test.

	
Secondary outcomes

	
For Cohort A, the PACT-Q2 score at Visit 2 and Visit 3 will be compared using paired t-test or Wilcoxon signed-rank test based on the distribution of the data.

	
For Cohort B, descriptive summary will be presented for PACT-Q1 score at baseline visit on all patients in Cohort B and by treatment (Pradaxa® or VKA).

Milestones:	
• IRB/IEC approval: 17 July 2017
	
• Start of data collection: 07 August 2017
	
• End of data collection: 27 September 2018
	
• Final report of study results: 20 December 2018

5. AMENDMENTS AND UPDATES

None.

6. MILESTONES

Milestone	Planned Date
IRB/IEC approval	17 July 2017
Start of data collection	07 August 2017
End of data collection	27 September 2018
Final report of study results	20 December 2018

7. RATIONALE AND BACKGROUND

Pradaxa® (dabigatran etexilate), one of the novel oral anticoagulants (NOACs), is a direct thrombin inhibitor first approved in Europe in 2008 for the prevention of stroke and systemic embolism in adult patients suffering from non-valvular atrial fibrillation (NVAF) with one or more risk factors. In 2010, the Food and Drug Administration (FDA) confirmed the findings of the RE-LY study in 18,000 patients, which led to the approval of Pradaxa® for stroke prevention in AF worldwide.^{1,2,3} In 2014, the FDA reported the study results comparing Pradaxa® to warfarin in 134,000 patients, and concluded that Pradaxa® was associated with a significantly reduced risk of ischaemic stroke and intracranial bleeding and a significant survival benefit compared with warfarin in elderly patients with NVAF.¹ Similar results were found in other observational studies, showing Pradaxa® was effective and safe with low rates of cardiovascular or major bleeding events.^{4,5,6}

According to the previous study results, the decision in clinical practice to use Pradaxa® or established vitamin K antagonists (VKAs) depends on many factors related to: (a) The patient: health status, comorbid and demographic conditions, perception of anticoagulant treatment, understanding of the burden of the disease, access to the medication, educational measures informing about medications, and reimbursement status. (b) The treating physician: stroke risk assessment, bleeding risk assessment, adherence to guidelines, access and use of medical education, and overall local health care system. These factors in the real-world clinical practice vary in countries with different health care systems; patients who newly start anticoagulation treatment versus those have had anticoagulation experience already; and the initiation versus the mid-term follow-up on Pradaxa®. According to National Health Insurance (NHI) in Taiwan, Pradaxa® is prescribed to a newly diagnosed NVAF patient with stroke or systemic embolism, left ventricular ejection fraction < 40%, symptomatic heart failure (New York Heart Association Class ≥ 2), age ≥ 75 years, or age ≥ 65 years with one of the following risk factors: diabetes mellitus, coronary artery disease (CAD), or hypertension. Pradaxa® should not be considered if the patient has valvular heart disease, stroke within 14 days, serious stroke within 6 months, the risk of increasing ischemia, creatinine clearance (CrCl) < 30 mL/min, active liver disease, or pregnant.

Although the clinical practice guide on the dosing and management of Pradaxa® is well established, the data on how patients perceive Pradaxa® treatment in the context of atrial fibrillation disease management only exist to a limited degree.⁷ In the RE-LY study, over the course of one year, all the anticoagulated patients without outcome events (e.g. strokes or major bleedings) had stable results in Health-Related Quality of Life (HRQoL). To further describe patient's perception of anticoagulant treatment when using Pradaxa® to prevent stroke and systemic embolism while suffering from NVAF in comparison to standard care using VKA, some patient convenience studies are conducted in Europe (and and Asia at present. However, such a non-interventional study (NIS) observing patients treated with Pradaxa® for stroke prevention in atrial fibrillation (SPAF) to assess treatment satisfaction has not been conducted in Taiwan. Due to the limited data on patients' perception of conventional VKA or Pradaxa® treatment in real world experience (RWE), it remains an interesting topic to address. Therefore, the observational study is proposed to describe the perception of

anticoagulant treatment according to the questionnaire—PACT-Q in the cohorts of patients switching from VKAs to Pradaxa® or newly initiating Pradaxa®/VKAs.

8. RESEARCH QUESTION AND OBJECTIVES

Objective 1

To describe the treatment perception from patients with non-valvular atrial fibrillation (NVAF) receiving Pradaxa® or VKA for stroke prevention by using the self-estimation questionnaire of PACT-Q during a 6-month study period.

Objective 2

To investigate the patient's characteristics.

Two cohorts of patients will be recruited:

Cohort A:

Patients who had been treated with VKA and have switched to Pradaxa®.

Cohort B:

Patients who are newly diagnosed with NVAF and initiated on either Pradaxa® or VKA.

9. RESEARCH METHODS

9.1 STUDY DESIGN

This is a non-interventional, single-country, multi-center study based on newly collected data. The study will enroll consented patients with NVAF in Taiwan with a previous VKA therapy, followed by switching to Pradaxa® (Cohort A) OR patients being newly diagnosed with NVAF and initiated on Pradaxa® or VKA (Cohort B). Patients will be followed up over an observation period of 6 months. Data will be collected at 3 time points:

1. Baseline (e.g., the enrolment date for Cohort A; the date of initiation on Pradaxa® or VKA for Cohort B).
2. 30 to 45 days after baseline (initiation period).
3. 150 to 210 days after baseline (continuation period).

9.2 SETTING

It is planned that data of approximately 1000 patients will be collected from approximately 20 medical centers or regional hospitals in Taiwan where Pradaxa® taken as one 110/150 mg capsule twice a day is listed as a prescription of SPAF in hospital formulary. Patients diagnosed with NVAF before the patient's baseline (inclusion) visit will be consecutively enrolled in the study. Selected subjects must meet all of the eligibility criteria described in Section 9.2.2.

After study initiation, the sites will include suitable patients where the decision for switching from VKA to Pradaxa® (Cohort A) or decision for initiation with Pradaxa® or VKA (Cohort B) has been made. Consecutive enrolment will be performed during whole recruitment period to minimize selection bias in the real-world practice.

The decision for therapy has to be made prior to and independently of enrolment into the study. Only after the treatment decision for the patient is made, the investigator can check and decide if a patient can be enrolled in Cohort A or Cohort B. Patients will then have to sign the informed consent before they can take part in the non-interventional study.

9.2.1 Study sites

Cardiologist and non-cardiologist sites regularly prescribing Pradaxa® and VKA for stroke prevention in NVAF according to the respective Summary of Product Characteristics (SmPCs) will participate.

Selected sites include around 20 medical centers or regional hospitals in Taiwan, from Northern to Southern area, with physicians and facilities that reflect the locally clinical practice. The site selection criteria will help to ensure that the patients recruited into this study will represent the population with NVAF receiving Pradaxa® or VKA for stroke prevention in Taiwan.

9.2.2 Study population

Inclusion criteria

Cohort A (patients switched from VKA to Pradaxa®)

- 1.A. Written informed consent prior to participation.
- 2.A. Female or male patients ≥ 20 years of age with a diagnosis of non-valvular atrial fibrillation (NVAF).
- 3.A. At least 3 months of continuous VKA treatment for stroke prevention prior to baseline assessment.
- 4.A. Patients switched to Pradaxa® prior to baseline assessment according to the physician's discretion and the Summary of Product Characteristics (SmPCs)/reimbursement criteria.

OR

Cohort B (patients newly initiated Pradaxa® or VKA)

- 1.B. Written informed consent prior to participation.
- 2.B. Female or male patients ≥ 20 years of age, newly diagnosed with NVAF, and no previous treatment for stroke prevention (no use of any OAC within 1 year prior to enrolment).
- 3.B. Patients initiated stroke prevention treatment with Pradaxa® or VKA according to the physician's discretion and the SmPCs/reimbursement criteria.

Exclusion criteria

1. Contraindication to the use of Pradaxa® or VKA as described in the SmPCs.
2. Patients receiving Pradaxa® or VKA for any other condition than stroke prevention in NVAF.
3. Current participation in any clinical trial of a drug or device.
4. Current participation in an AF-related registry, e.g. the Gloria AF program.

Withdrawal criteria

Every patient has the right to withdraw consent at any time during the study, without the need for justification or any impact on the routine therapy. A patient is considered permanently discontinued or withdrawn from treatment if he/she does not complete the treatment with Pradaxa® or VKA in the 6-month study period or did not perform all three assessments. Withdrawal criteria includes:

1. Patients withdraw informed consent.
2. Patients lost to follow-up.
3. Any pathological event, adverse event, or any change in the patient's status giving an indication to the physicians that further participation in the study may not be the best interest of the patient.

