9.2.3 Study visits

Collection of patient data should be managed during routine practice visits. The time schedule below can only be a recommendation; if a patient does not visit the site at these time points, no visit will be conducted solely for study purposes. Visits must be performed face-to-face and cannot be performed by phone, email, or fax, as the patient has to complete the self-administered questionnaires (PACT-Q). The planned collection time points are as follows:

1. Baseline (e.g., the enrolment date for Cohort A; the date of initiation on Pradaxa® or VKA for Cohort B)
2. 30 to 45 days after baseline (initiation period)
3. 150 to 210 days after baseline (continuation period)

Data will be collected and recorded on the CRF at baseline and follow-up visits according to **Table 1**, if available.

Remark: This is a non-interventional, observational study, all the tests collected at baseline and subsequent visits will be performed as judged appropriate by the treating physicians, and the results of interest will be recorded only if they are available. This study does not require additional tests or examinations to be performed throughout the entire study period.

Baseline visit (Visit 1):

No data collection for study purposes must be performed unless the patient has consented to participate in the study. Once the patient has signed the informed consent form, the patient is considered to be enrolled in the study and patient details should be recorded on the enrolment log.

The following procedures will be performed at the baseline visit, and data will be collected from the medical chart and recorded on the CRF, **if available**:

- Sign informed consent form.
- Review of inclusion and exclusion criteria, and record date of inclusion.
- Collection of reimbursement status (reimbursed, partially reimbursed, or private pay).
- Collection of demographic data: age, gender, race, education level, height, weight[&], and BMI.
[&]Weight will be used to calculate BMI and creatinine clearance (CrCl).
- Collection of concomitant diseases/comorbidities in the medical history and at baseline.

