- Collection of concomitant diseases/comorbidities,⁸ risk factors,^{9,10} and medical history related to NVAF prior to enrolment, including diabetes mellitus, hypertension, ischaemic heart disease, congestive heart failure, left ventricular dysfunction, stroke, transient ischaemic attack, thromboembolism, vascular disease (myocardial infarction, peripheral artery disease, and complex aortic plaque), abnormal renal function,

abnormal liver function (e.g. cirrhosis), bleeding (e.g. prior major bleeding, predisposition to bleeding/anemia), and alcohol usage. These data will be used to calculate CHA₂DS₂-VASC score and HAS-BLED score[#].

- Collection of current concomitant therapies within 1 month prior to enrolment. Detail information (e.g. indication, start/stop date or ongoing, dosage, route, unit, and frequency etc.) will be recorded if available.
 - For the concomitant therapy as an element for CHA₂DS₂-VASC score or HAS-BLED score calculation^{9,10} including chronic dialysis or renal transplant due to abnormal renal function and medication usage predisposing to bleeding (antiplatelet agents or nonsteroidal anti-inflammatory drugs (NSAIDs)), information prior to enrolment will only be collected as **active/past or never occurred**.
- Collection of serum creatinine, if available, to calculate creatinine clearance (CrCl). The most updated data of serum creatinine assessed prior to enrolment will be collected. CrCl will be calculated according to Cockcroft-Gault formula (using weight collected at the baseline visit and the most updated serum creatinine assessed prior to enrolment).
- Collect the most updated data of lab assessment assessed prior to enrolment for CHA₂DS₂-VASC score and HAS-BLED score calculation^{9,10}. The lab assessments include renal function test (CrCl, as described above), liver function tests (bilirubin, aspartate aminotransferase (AST), alanine aminotransferase (ALT), and alkaline phosphatase (AP)), and international normalized ratio (INR), including prothrombin time (PT).
- For Cohort A only: Collect duration of previous treatment with VKA.
- For Cohort A only: Collect reasons for switching from VKA to Pradaxa[®].
- Document the dosing of Pradaxa[®].
- Patients will be asked to complete the following patient related questionnaires:
 - PACT-Q1 (Cohort B only)
 - PACT-Q2 (Cohort A only)

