9.3 VARIABLES

9.3.1 Exposures

Currently, Pradaxa® and VKA have been approved for treating NVAF patients for stroke prevention. The use of Pradaxa® and VKA will be according to the SmPCs and physician's discretion. Prescription of Pradaxa® will be collected and recorded on the CRF during the

observational period, if available, including start/end date, dose, and the reason for dose adjustment or interruption.

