9.3.5 Description and justification of patient questionnaires (PACT-Q[®])

The Perception of Anticoagulant Treatment Questionnaire (PACT-Q) was developed as a means to investigate patients' satisfaction with anticoagulant treatment and treatment

convenience in patients with deep venous thrombosis (DVT), pulmonary embolism (PE), or atrial fibrillation (AF).^{13,14} The PACT-Q is a self-administered questionnaire. It can be completed in about 10 minutes. No specific training is required to complete this document.

The original PACT-Q consists of 2 parts and contains 27 items:

1. The PACT-Q1 is composed of a single dimension (7 items), covering the expectations of patients regarding their anticoagulant treatment, and is to be administered before treatment initiation. Only patients in Cohort B (newly initiator) will receive the PACT-Q1 questionnaire at baseline.
2. The PACT-Q2 is composed of 3 dimensions covering: convenience (11 items), burden of disease and treatment (2 items), and anticoagulant treatment satisfaction (7 items). The PACT-Q2 is to be administered to patients once treatment is ongoing. The patients in Cohort A (switchers) will receive PACT-Q2 at all the 3 visits, while the ones in Cohort B (initiators) will receive the questionnaire at Visit 2 and Visit 3.

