9.7.3 Safety analysis

Safety analyses will be performed separately for Cohort A and Cohort B, and will include all enrolled patients with an actual follow-up. Statistical analysis and reporting of AEs (i.e. Pradaxa® relevant ADR (serious and non-serious), fatal AEs, and pregnancies) will be descriptive in nature and based on BI standards. No hypothesis testing is planned. The assessment of safety will be based mainly on the frequency of adverse events, which includes

all serious adverse events. All adverse events will be summarized with the coding term, severity, and relationship to study drug by frequency tables with the counts and percentage.

In addition, occurrences of Pradaxa® relevant ADRs will be analyzed relative to the number of patients treated as well as observed person-years (i.e. time at risk). If no concurrent Pradaxa® treatment is administered, then events occurring within a washout period of 3 days after discontinuation of Pradaxa® treatment will be assigned to the last treatment given. This washout period will also be included as time at risk for derivation of total person-years. ADRs that deteriorate under treatment will also be considered as “treatment emergent”. Events occurring prior to first intake of Pradaxa® treatment prescribed at baseline, during periods without Pradaxa® treatment (excluding washout periods), or after the end of the 6-month follow-up (excluding washout periods) will not be considered treatment emergent events, and will not be included in the summary tables.

Furthermore, serious adverse events will be listed with event narration. Adverse events will be coded using the latest version of Medical dictionary for regulatory activities (MedDRA) terminology.

The following parameters will be included in the safety analyses:

- Adverse drug reactions
- Adverse drug reactions leading to discontinuation of anticoagulation treatment
- Serious adverse drug reactions
- Adverse events leading to deaths

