## 10 DEFINITION AND DETERMINATION OF ANALYSIS

### VARIABLES

#### 10.1 Treatment Exposure and Compliance

Treatment duration will be counted from the date of visit 1 to the discontinued date in the Pradaxa® / VKA Discontinuation page. For those continuing using study drug, Treatment duration will be counted from the date of visit 1 to the date of visit 3. Treatment duration will be summarized as continuous variables. The reason for treatment discontinuation will be summarized as categorical data.

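### Cohort A baseline PACT-Q2: criterion 4.A puts the switch to Pradaxa before it, other sections put the start at or about it, and neither document names the drug it rates

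*Protocol*

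**What the plan says.** Protocol 9.2.2 and SAP 7.2.1 set two timing conditions for Cohort A. Criterion 3.A asks for "At least 3 months of continuous VKA treatment for stroke prevention prior to baseline assessment". Criterion 4.A asks for "Patients switched to Pradaxa® prior to baseline assessment according to the physician's discretion". The objectives (Protocol 8, SAP 6.1) also describe these patients as having already switched.

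Visit 1 is defined in Protocol 9.2.3 as "Baseline (e.g., the enrolment date for Cohort A; the date of initiation on Pradaxa® or VKA for Cohort B". Cohort B's baseline is therefore tied to drug start and Cohort A's is not.

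Cohort A completes PACT-Q2 at all three visits. On administration, Protocol 9.3.5 says "The PACT-Q2 is to be administered to patients once treatment is ongoing", without naming the treatment. The primary change is the Visit 2 score minus the Visit 1 score, and the last-visit score minus the Visit 1 score (Protocol 9.3.2.1, SAP 10.2 and 11.3).

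Other sections describe the start of Pradaxa differently. Protocol 9.7.3 and SAP 11.5 set aside "Events occurring prior to first intake of Pradaxa® treatment prescribed at baseline". SAP 10.1 states "Treatment duration will be counted from the date of visit 1". Visit 2, at 30 to 45 days, is called the initiation period for both cohorts. Protocol 9.2 lets sites include patients once the decision to switch has been taken.

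**The concern.** A change score means something only if its reference is known. The Visit 1 PACT-Q2 is the reference for both Cohort A primary comparisons. If it rates VKA, the change describes moving from VKA to Pradaxa. If it rates Pradaxa, the change describes how perception develops during Pradaxa treatment. The study title sets conventional against novel anticoagulation, so the first meaning is the one most readers will assume.

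The planned conclusion does not guard against this. SAP 11.6 would report p < 0.05 as a significant change in patients on either drug, with no reference drug named. If every baseline score were given on Pradaxa, neither a positive nor a null Cohort A result would say anything about VKA versus Pradaxa.

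**Working it through.** The plan gives no figure to reproduce on this point: there is no SD, no expected change and no interval since the switch. The check is therefore a comparison of the passages.

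**1. Where each passage puts the start of Pradaxa in Cohort A**

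| Source | Start relative to Visit 1 |
|---|---|
| Criterion 4.A; objectives | Before, with no limit on the interval |
| Protocol 9.7.3, SAP 11.5 | Prescribed at baseline, first intake at or after it |
| SAP 10.1 | Duration begins at Visit 1, no distinction by cohort |
| Visit 2 named the initiation period | Start at or about baseline |
| Protocol 9.2 | Only the decision is needed; fits either order |

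The clearest conflict is between 4.A and the safety sections. SAP 10.1 could be a simplified exposure rule covering both cohorts, so it weighs less.

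**2. Whether another passage settles it**

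- Criterion 3.A can mean VKA running up to baseline, or an earlier three-month spell. The first is the more natural reading.
- Protocol 9.3.5 requires an ongoing treatment at the time of PACT-Q2. VKA or Pradaxa could be that treatment.
- The Visit 1 item "For Cohort A only: Collect duration of previous treatment with VKA" calls the VKA treatment previous, which fits 4.A but does not exclude a switch on that day.
- If switched means prescribed but not yet taken, the passages agree. No passage says so.

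**3. What the primary change measures under each reading**

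- 4.A read literally, with the form rating the current drug: Visit 2 or last visit minus Visit 1 is later minus early Pradaxa.
- Pradaxa starting at or just after Visit 1, with the form rating the current drug: the same subtraction is Pradaxa minus VKA.
- Sites differing in how they applied 4.A: the cohort mean is an average of the two, with unknown weights.

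The secondary Cohort A comparison (last visit against Visit 2) does not use the Visit 1 score.

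**4. Exposure**

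Time on Pradaxa = duration counted from Visit 1 + (date of Visit 1 − date of first intake). Under literal 4.A the bracket is positive and has no stated upper limit, so the SAP 10.1 duration is too short by that amount. If first intake is at Visit 1 the bracket is zero.

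**5. Analysis set**

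The Full Analysis Set is all eligible patients (SAP 8.3; the same population in Protocol 9.7). Under literal 4.A, a patient scored before first intake is not eligible and falls outside it. These are the patients whose baseline would most plainly rate VKA.

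**6. Whether the planned data could separate the cases**

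Pradaxa prescription data are planned for the "observational period, if available, including start/end date, dose" (Protocol 9.3.1), so a start before enrolment may not be captured. Protocol 9.10.2.1 lists visit dates and prescription of study medication among the data drawn from source documents, so the date may be recoverable. No analysis in the SAP uses it.

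**The case against.** The best defence is that 4.A is loosely worded and the rest of the plan points to a start near baseline. The initiation-period label, the safety sections, the SAP exposure rule and the natural reading of 3.A all lean that way. Criterion 4.A can then be taken as the safeguard of Protocol 9.2, that treatment is decided before and independently of enrolment. On that reading the ongoing treatment at Visit 1 is VKA and the endpoint is sound. Much of this stands, and it is why the point asks for reconciliation and does not assert a failed design. It does not close the matter: 4.A is an eligibility rule that sites must apply as written, and the objectives repeat it.

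The rated drug may also be stated on the Taiwanese PACT-Q2 form (Protocol Annex 1) or in the administrative memorandums that SAP 5 mentions. Neither was seen. A form that asked about current treatment would still leave open which drug each patient was taking.

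The protocol calls the study essentially descriptive, and the matched Cohort B analysis supplies its own Pradaxa-versus-VKA comparison. Both are true and limit the consequence. Even so, the Cohort A change is a primary outcome tested at 0.05, and a descriptive change also needs a defined reference.

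A reader might go further and infer that the Cohort A endpoint is a mixture, or that the effect is diluted towards zero by some calculable amount. The documents support neither. A mixture arises only if sites applied 4.A differently, which no passage shows. Any dilution figure would need the share of baselines on Pradaxa and the change during Pradaxa treatment, and neither is given.

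**Conclusion.** The inconsistency is in the text and touches a primary outcome. Criterion 4.A and the objectives place the switch before Visit 1; Protocol 9.7.3, SAP 11.5, SAP 10.1 and the Visit 2 label place the start at or about it; and neither document names the drug that the Visit 1 PACT-Q2 rates. Taken literally, 4.A makes the Cohort A primary change a within-Pradaxa change and understates exposure counted from Visit 1. If practice varied between sites, the change combines two contrasts.

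No magnitude can be given, and the bias could run in either direction. Which timing was intended is for the sponsor to say. Confidence is medium, because the questionnaire form, the CRF and the memorandums were not available. The Cohort B comparison is untouched. The point should be fixed before the Cohort A scores are analysed.

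**What to change.** 1. The sponsor reconciles criterion 4.A with Protocol 9.2, Protocol 9.7.3, SAP 10.1 and SAP 11.5, and states which treatment the Visit 1 PACT-Q2 rates. Eligibility and treatment timing need not change for this.
2. The SAP uses the date of first Pradaxa intake for every Cohort A patient, including starts before enrolment, taken from the CRF or from charts, and counts treatment duration from that date. For ADR rates the SAP should say how time before consent is handled, because Protocol 11.2 collects ADRs only from consent onwards.
3. The SAP reports the number of patients and the PACT-Q2 change separately for Visit 1 scores completed on or before first intake and after it. It states how the reconciled 4.A affects membership of the Full Analysis Set in each group.
4. Any VKA-to-Pradaxa statement rests only on patients whose Visit 1 score rates VKA. The date alone does not prove this, since a patient scored soon after switching might still have VKA in mind, so step 1 is needed as well. If there are no such patients, or few, the Cohort A endpoint is labelled as change during Pradaxa treatment.

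The cost is one clarifying statement, one date per Cohort A patient (about 300 planned, possibly already on the CRF), one SAP flag and split tables. Planned data collection ended on 27 September 2018 (Protocol 6), so missing dates would have to come from charts. The downside is that fewer patients, possibly none, would support a VKA-to-Pradaxa statement from Cohort A.
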